1 PROTOCOL SUMMARY

Background and Rationale

Topical diclofenac products are well established globally for the treatment of pain and inflammation due to acute trauma as well as for the relief of pain associated with non-serious osteoarthritis (OA) of the peripheral joints e.g. knee and fingers. The originator product diclofenac diethylamine (DDEA) 1.16% gel (Voltarol Emulgel in the UK, and generic name of DDEA Emulgel was registered in China) was first registered in 1985 in Switzerland and Romania for use at a dose of 2-4 g applied three to four times daily and is currently registered in over 130 countries of which over 80 countries market this product as over-the-counter (OTC).

As part of the global expansion for the product, China has been identified as a desirable market for registration of DDEA 2.32% gel. The identified registration pathway in China for the DDEA 2.32% gel is variation specifying addition of a new strength to the already registered DDEA 1.16% gel (License Number H20181225/H20181226, firstly issued on March 12, 2013), with the same indications as currently registered for DDEA 1.16% gel, i.e. for the relief of mild to moderate pain in muscles, soft tissues, and joints, e.g. muscles or soft tissue pains caused by sprain, pulling injury, contusions, strain, waist-back injury and various arthralgia etc, and for symptomatic treatment of osteoarthritis.

In support of the proposed registration, the National Medical Products Administration (NMPA) approved a clinical trial application (CTA) on November 06, 2016 (CTA No. 2016L09875). The approved CTA stipulated that a non-inferiority study assessing the efficacy and safety of the DDEA 2.32% versus that of the registered DDEA 1.16% should be conducted in a local population.

To this effect, GSKCH intends to conduct a randomized, double blind, multi-center, active controlled, parallel group, non-inferiority study to evaluate the efficacy and safety of DDEA 2.32% gel applied twice daily versus DDEA 1.16% gel applied four times daily in subjects with ankle sprain in China.

Objective(s)	Endpoint(s)
Primary	
To demonstrate non-inferiority between DDEA 2.32% and DDEA 1.16% with regard to pain relief after acute ankle sprain	Change from baseline in pain on movement (POM) on Day 5 of treatment as assessed by a 100 mm VAS scale
Secondary	
To assess safety of DDEA 1.16% and DDEA 2.32% gels after 1 week of use	Number, incidence, and severity of adverse events following dosing with study medication
To assess efficacy of treatments for pain relief as measured by POM on Days 3 and 8	Change from baseline of POM on VAS on Day 3 and Day 8 of treatment assessed by 100 mm VAS scale
To assess efficacy of treatments for inflammation of the affected ankle as measured by pressure algometry on Days 3, 5, and 8	Change from baseline in tenderness as measured by pressure algometry on Days 3,5, and 8
To assess efficacy of treatments for inflammation of the affected ankle as measured by pressure algometry on Days 3, 5, and 8	Difference between measurement in affected ankle and contralateral ankle on Days 3,5,and 8
To assess efficacy of treatments for ankle joint function as measured on the Karlsson Scoring Scale	Change from baseline in Ankle Joint Function (Karlsson Scoring Scale) on Days 3,5, and 8

Objectives and Endpoints

To assess efficacy of treatments for swelling of affected ankle as measured by Figure of Eight Method	Change from baseline in circumference of affected ankle as measured by Figure of Eight method on Days 3,5, and 8	
To assess efficacy of treatments for swelling of affected ankle as measured by Figure of Eight method	Difference between circumference of affected ankle to unaffected ankle by Figure of Eight method on Days 3, 5, and 8	
To assess efficacy of treatments for effect on pain intensity as measured by Sum of Pain Intensity Difference (SPID)	SPID from 0 – 24 hours post first dose (Day 1) and from 96 – 120 hours post first dose (Day 5)	
To assess effect of treatments for effect on pain relief as measured by Total Pain Relief (TOTPAR)	TOTPAR from 0 – 24 hours post first dose (Day 1) and from 96 – 120 hours post first dose (Day 5)	
To assess the use of rescue medication among subjects	Number of tablets used to treat ankle pain and overall	
To assess the use of rescue medication among subjects	Number of days on which rescue medication was used to treat ankle pain and overall	

Study Design

This is a Phase III, randomized, double blind, multi-center, active controlled, 2 treatment arm, parallel group, non-inferiority study to evaluate the efficacy and safety of diclofenac diethylamine 2.32% gel applied twice daily versus diclofenac diethylamine 1.16% gel applied four times daily for 1 week in subjects with acute ankle sprain.

To qualify, subjects must experience an acute Grade I -II sprain of the ankle within the past 24 hours. Subjects should be randomized as soon as possible after the injury.

Subjects who meet all of the inclusion criteria and none of the exclusion criteria will be randomized in a 1:1 ratio to one of the following two treatment arms:

Treatment Schedule

Treatment Arms	Morning (Upon Rising)	Noon	Late Afternoon (evening)	Late Evening (bed time)
DDEA 2.32% four times daily	DDEA 2.32% gel	Placebo gel	DDEA 2.32% gel	Placebo gel
DDEA 1.16% four times daily	DDEA 1.16% gel	DDEA 1.16% gel	DDEA 1.16% gel	DDEA 1.16% gel

Approximately 300 subjects (150 in each group) with acute ankle sprain are to be randomized. All subjects will receive four (4) tubes of study drug, for treatment in morning, noon, late afternoon, and late evening, respectively. The very first dose of study drug will be applied at the study center. The subjects will be instructed to apply the gel topically with the finger tips (for approximately 1 minute) in the morning, at noon, late afternoon, and late evening for 7 days. Each tube will be labeled for use at one of these 4 times.

After the randomization visit (Visit 1/baseline visit), subjects will return to the study site for post baseline visits, namely Visit 2, Visit 3, and Visit 4 to complete efficacy and safety assessments. Baseline safety laboratory test blood samples will be taken. End of study safety laboratory tests will also be taken at Visit 4, or in case of early termination. In addition, subjects (ex-clinic) will assess pain intensity and pain relief at frequent intervals on Day 1 and then at

Diclofenac Diethylamine 2.32% Study 211206 Protocol Amendment 1

each study drug application throughout the rest of the study. The schedule of visits is described below.

Study c	enter	visits	per	subj	ect:
---------	-------	--------	-----	------	------

Screening / Randomization visit [Visit 1]	Day 1 (0 h)
1 st interim visit [Visit 2]	Day 3 (48 \pm 4 h after initiating treatment)
2nd interim visit [Visit 3]	Day 5 (primary endpoint measurement)
	$(96 \pm 4 h after initiating treatment)$
Final visit [Visit 4]	Day 8 ± 1 d
	$(7 \pm 1 \text{ days after initiating treatment})$

Study Products

The following products will be administered in this study:

	Active Treatment ^a	Active Comparator ^b	Placebo Product for Blinding of Active Treatment ^a
Product Name	DDEA 2.32% Gel	DDEA 1.16% Gel	Placebo gel - 0% diclofenac gel
Pack Design	2 x 50 g tubes	4 x 50 g tubes	2 x 50 g tubes
Dispensing Details	1 kit per subject at Visit 1ª	1 kit per subject at Visit 1 ^b	1 kit per subject at Visit 1ª
Product Master Formulation Code (MFC)	CCI	EC	CCI
Dose/Application	Gel – 5 cm (2 g) on 200 cm ²	Gel – 5 cm (2 g) on 200 cm ²	Gel – 5 cm (2 g) on 200 cm ²
Route of Administration	Topical	Topical	Topical
Usage Instructions	Two times daily (BID) (morning and late afternoon)	Four times daily (QID)	Two times daily (BID) (noon and late evening)

^a The study products for the Active Treatment and Placebo Product for Blinding of Active Treatment will be provided in a single kit containing 4 tubes (2 tubes of each study product)

^b The study product for the Active Comparator will be provided in a single kit containing 4 tubes (4 tubes of Active Comparator product)

Rescue medication (paracetamol, up to 2000 mg daily) will be allowed during the study, except for the 6 hours prior to each study visit and 12 hours prior to Visit 3.

Type and Planned Number of Subjects

Approximately 300 subjects who present to the study within 24 hours of suffering a Grade I-II ankle sprain will be randomized to ensure at least 240 evaluable subjects complete the study for the (PP) per protocol analysis population.

Approximately 120 subjects per treatment arm has been determined to provide 80% power to demonstrate non-inferiority of DDEA 2.32% gel b.i.d with DDEA 1.16% gel q.i.d. by comparing the two-sided 95% confidence interval (CI) of the difference in mean change from baseline of VAS POM score between the two products with the non-inferiority margin of 13 mm. This assumes a treatment standard deviation of 22mm and allows for a possible small true treatment difference of 5mm in favor of DDEA 1.16%.

The primary efficacy endpoint will be the change from baseline in POM on Day 5 of treatment as assessed by a 100 mm VAS scale.

The following primary non-inferiority hypothesis will be tested for DDEA 2.32% vs DDEA 1.16%:

The null hypothesis is Diclofenac 2.32% DDEA Gel administered BID is inferior to Diclofenac 1.16% DDEA gel administered QID with the alternative hypothesis being Diclofenac 2.32% DDEA Gel administered BID is non-inferior to Diclofenac 1.16% DDEA gel administered QID.

Diclofenac 2.32% DDEA Gel administered BID will be declared non-inferior to Diclofenac 1.16% DDEA gel administered QID if the upper limit of the two-sided 95% CI of the difference between their mean changes from baseline VAS POM responses is less than the established margin of 13 mm.

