9.2.1 Ankle Swelling

Ankle swelling is evaluated at Visits 1-4 by the Figure-of-eight-method, a common procedure to assess ankle size. The method has been validated on healthy volunteers with an intra-class correlation coefficient of 0.99 for inter-tester reliability and 0.99 for intra-tester reliability [Tatro Adams 1995, Petersen 1999, Friends 2008].

The Figure-of-eight-method is reproduced by using bony landmarks about the ankle. Common sites of ankle sprain swelling are the anterior talofibular ligament, calcaneofibular ligament, and anterior tibiofibular ligament. Because the tape spans each of these anatomical areas, the figure-of-eight-method may offer a more accurate clinical assessment of ankle swelling.

In detail: a one-quarter-inch wide (about 63 mm), retractable, plastic tape measure is utilized to obtain the measurements of each subject's ankle. All measurements are recorded in cm. Each subject is seated comfortably in a long sitting position with both feet extended beyond the end of the plinth in a slight dorsiflexion position. The figure of eight-method is applied to both feet and the tape measure is wrapped around the ankle along the following course: the beginning of the tape is placed midway between the tibialis anterior tendon and lateral malleolus and is then continued across anatomically defined points in the form of a figure of eight around the ankle joint (for details [Tatro Adams 1995]). The tape localization of the first measurement should be marked with an appropriate marker.

Each ankle is measured three times and the average is calculated. The difference in this average between ankles tracks the natural course of disease.

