9.2.3 Tenderness

'Tenderness' is the sensation of pain expressed by a subject when pressure is applied to the body. A more precise term is 'pressure pain threshold', the minimum pressure required to cause pain. Tenderness or pressure pain threshold is one of the major palpatory signs used by practitioners for diagnostic and treatment assessment purposes. Tenderness can be quantified with an algometer (pressure pain meter). It measures the amount of pressure a subject can endure before a pain sensation is elicited. Algometers have been used extensively to measure the efficacy of therapeutic interventions for the treatment of pain [Fischer 1987, Ohrbach 1989, Galer 2000,

GlaxoSmithKline Consumer Healthcare Confidential Template Version Effective: 18-May-18 (CCR #11475) Page **39** of **64**

Wetzel 2002, Chesterton 2003]. The reliability of repeated measurements of pressure pain threshold has been demonstrated [Fischer 1987, Nussbaum 1998].

Tenderness will be measured by calibrated algometers in an area of 1 cm^2 at the centre of the injured area. The position of measurement will be marked with a water resistant marker on subjects' skin to ensure consistent measuring points throughout the study. The investigator will apply the pressure gauge to the marked tender point of maximum sensitivity by placing the gauge at a 90° angle vertical to the skin.

The subject is instructed to indicate the onset of pain (pressure pain threshold) with a verbal cue such as "Yes" or "Stop". Measurements will be performed with covered scale so that investigator and subject cannot see the values. They will be evaluated after measurement.

For assessment of a treatment effect the tenderness of the treated painful area has to be compared with the tenderness at the corresponding anatomical position of the healthy uninjured contralateral side.

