12.2.6 Secondary Analysis(es)

Secondary outcome measures (endpoints) include:

- Change from baseline of POM on VAS on Days 3 and 8 respectively
- Tenderness measured by pressure algometry on Days 3, 5 and 8 (change from baseline and difference between the measurement in injured area and contralateral area)
- Change from baseline Ankle Joint Function (Karlsson Scoring Scale) on Days 3, 5 and 8
- Circumference measurement of swelling (change from baseline in circumference of affected ankle and comparison to non- affected ankle by Figure of Eight method on Days 3, 5 and 8)
- Pain Intensity and Pain Relief
 - Sum of Pain Intensity Difference (SPID) From hours 0 24 post first dose (corresponding to Day 1) and from hours 96 120 post first dose (corresponding to Day 5)
 - Total Pain Relief (TOTPAR) From hours 0 24 post first dose (corresponding to Day 1) and from hours 96 120 post first dose (corresponding to Day 5)

TOTPAR and SPID will be calculated as weighted sums of the Pain Relief Score and Pain Intensity Difference at each timepoint respectively:

 $TOTPAR = \Sigma R_t^x (time_t - time_{t-1})$

Where R_t = the pain relief score at time t and time t = time in hours post first dose

 $SPID_t = \Sigma PID_t (time_t - time_{t-1})(h)$

Where PI is pain intensity

- Use of rescue medication, for ankle sprain and overall
 - Total number of tablets used
 - Total number of days on which rescue medication was used

Figures will show the time course of outcomes by treatment group for key quantitative outcomes.

For POM, Karlsson score, tenderness, swelling and diary assessments (SPID and TOTPAR), an ANCOVA model including treatment group and center as main effects, and the baseline value as covariate (those outcomes for which there is a baseline) will be used for analysis, with the treatment difference and 95% confidence interval (two-sided) presented for each assessment.

Use of rescue medication (number of tablets and days used) will be compared between treatments using the CHM method (modridit scores) stratified by center, with the median treatment differences and 95% confidence intervals (2-sided) presented using Hodges-Lehmann estimation.

These secondary endpoints will be analyzed using the per protocol and mITT populations.

GlaxoSmithKline Consumer Healthcare Confidential Template Version Effective: 18-May-18 (CCR #11475) Page **54** of **64**

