## 4.6 Analysis of Secondary Objectives

## 4.6.1 Efficacy (Secondary)

All the secondary endpoints POM at day 3 and 8, Karlsson score, tenderness, swelling and diary assessments (SPID and TOTPAR) will be analyzed using an ANCOVA model with treatment and center as fixed effect, baseline assessment for the corresponding endpoints as covariate. Treatment differences and two-sided 95% CI will be presented.

The secondary efficacy analyses will be performed and also be listed on mITT and PP population.

- Change from baseline of POM (CRF page: Pain on Movement; VAS score will be obtained from VASSCRL) on VAS on days 3 and 8 respectively (PPD).
- Tenderness measured by pressure algometry on days 3, 5 and 8 which will be analysed using change from baseline and difference between the measurement in injured area (CRF page: Tenderness; measurement for study ankle : QS\_INJA) and contralateral area (CRF page: Tenderness; measurement for study ankle : QS\_CLTA) (**PPD**)...
- Change from baseline Ankle Joint Function (Karlsson Scoring Scale; CRF page: Ankle Joint Function: Variable : Total Score KSSTS) on days 3, 5 and 8 (PPD)...
- Circumference measurement of swelling on days 3, 5 8 which will be analysed using change from baseline in circumference of affected ankle and comparison to non-affected ankle by Figure of Eight method (CRF Page:Ankle swelling; Variables: FOEMINSC and FOEMCASC respectively.) (PPD ;)..
- Pain Intensity and Pain Relief (CRF Page: Subject Diary(Day 1/5) ; variables will used to calculate the Pain Intensity and Pain Relief are DPI and DPR respectively for each timepoint (DSTMPT))
- Pain Intensity (PPD
  - Pain intensity will be analysed based on the Sum of Pain Intensity Difference (SPID). SPID is defined as from 0 -24 hours post first dose corresponding to day 1 and from 0-24 hours post first dose corresponding to day 5.
  - SPIDt=>PIDt(timet-timet-1)(h), where, PIDt=pain intensity score (DPI from CRF page corresponding to day); timet=time in hours post first dose

GlaxoSmithKline Consumer Healthcare Confidential

Page 23 of 36

211206

Statistical Reporting and Analysis plan Draft V2.0 20JAN2021

- Pain Relief (**PPD** 
  - Pain relief will be analysed based on the Total Pain Relief (TOTPAR). TOTPAR is defined as from 0-24 hours post first dose corresponding to day 1 and from 0-24 hours post first dose corresponding to day 5.

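### Adding the healthy ankle's Visit 1 value to the ANCOVAs for change in swelling and tenderness would narrow their confidence intervals at almost no cost; the planned models are valid without it

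*Protocol*

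**What the plan says.** The objectives tables (Protocol 1 and 3, SAP 1.2) give swelling and tenderness two secondary endpoints each.

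- **Change in the affected ankle:** "Change from baseline in circumference of affected ankle as measured by Figure of Eight method on Days 3,5, and 8" and "Change from baseline in tenderness as measured by pressure algometry on Days 3,5, and 8".
- **Side difference:** "Difference between circumference of affected ankle to unaffected ankle by Figure of Eight method on Days 3, 5, and 8" and "Difference between measurement in affected ankle and contralateral ankle on Days 3,5,and 8".

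Protocol 12.2.6 analyzes all of them by ANCOVA with treatment group and center, and "the baseline value as covariate (those outcomes for which there is a baseline) will be used for analysis". SAP 4.6.1 words the covariate as "baseline assessment for the corresponding endpoints as covariate". For the change endpoints, that is the affected ankle's Visit 1 value. Each assessment is reported as a treatment difference with a two-sided 95% CI, and no margin or power is stated for it.

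On data collection, Protocol 9.2.1 applies the figure-of-eight measurement to both feet at Visits 1-4 and adds that "The difference in this average between ankles tracks the natural course of disease". Protocol 9.2.3 says that, to assess a treatment effect, "the tenderness of the treated painful area has to be compared with the tenderness at the corresponding anatomical position" on the uninjured side. The Schedule of Activities places tenderness at Visit 1, and the SAP names a contralateral variable (QS_CLTA). A contralateral tenderness reading at Visit 1 is therefore implied, though not stated outright.

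**The concern.** The circumference of a sprained ankle is foot size plus swelling, and only the swelling can resolve. A pressure pain threshold on the injured side likewise combines the person's usual threshold with the loss caused by the injury. The affected ankle's baseline cannot separate the two parts; the pair of ankles can. A covariate improves precision only as far as it predicts the outcome, and what predicts the change is the initial injury component.

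At stake is the width of the reported intervals for these secondary endpoints on Days 3, 5 and 8. In a non-inferiority trial such intervals are read as supporting evidence that no important efficacy is lost, so needless width weakens that support.

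**Working it through.** **The plan's own figure.** The documents give no sample size, SD or correlation for swelling or tenderness. The only figure is for the primary endpoint: n per arm = 2(1.96 + 0.84)² × 22² / (13 − 5)² ≈ 119, against 120 stated. It reproduces and is untouched by this point.

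**Model (all inputs assumed).** Let F be the SD of foot size (or usual threshold), S the SD of the initial injury component, r the fraction of it remaining at follow-up, U the SD of new variation in recovery, E the SD of measurement error and A the SD of natural left-right asymmetry. Y is the change in the affected ankle. Center is left out of the formulas.

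- Var(Y) = (1 − r)²S² + U² + 2E²
- Covariance of Y with the affected baseline: c = −(1 − r)S² − E²
- Variance of the affected baseline: VA = F² + S² + E²
- Variance of the contralateral baseline: VC = F² + A² + E²
- Residual variance, planned model: V1 = Var(Y) − c²/VA
- Residual variance with both baselines: V2 = Var(Y) − c²·VC/(VA·VC − F⁴)
- CI width ratio = √(V2/V1)

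**Circumference, central case** (F = 3, S = 0.8, U = 0.4, E = 0.2 cm, r = 0.5, A = 0):

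- Var(Y) = 0.16 + 0.16 + 0.08 = 0.40; c = −0.32 − 0.04 = −0.36; VA = 9.68; VC = 9.04.
- The affected baseline's correlation with initial swelling is 0.8/√9.68 = 0.26.
- V1 = 0.40 − 0.1296/9.68 = 0.387, so the planned covariate removes about 3% of the variance.
- V2 = 0.40 − 0.1296 × 9.04/(87.507 − 81) = 0.220, which is 43% below V1.
- SE at 120 per arm, √(2V/120): 0.080 cm planned, 0.061 cm with both baselines. The CI is about 25% narrower.
- With the baseline side difference as the single covariate, the residual variance is 0.40 − 0.1296/(0.64 + 0.08) = 0.220, practically the same.

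**What moves the result.**

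- Asymmetry A = 0.4 cm: VC = 9.20 and V2 = 0.252, so the CI is about 19% narrower.
- Recovery variation U = 0.3 cm (A = 0): V1 = 0.317, V2 = 0.150, about 31% narrower. U = 0.6 cm: V1 = 0.587, V2 = 0.420, about 15% narrower.

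**Circumference, grid.** F 2-4, S 0.5-1.0, r 0.3-0.7, U 0.2-0.6, E 0.1-0.3, A 0.3-0.5. The CI is 2-57% narrower, median 16%. The planned covariate alone removes 0.1-18% of the variance in change, median 3%.

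**Tenderness, illustrative case** (F = 12, S = 10, U = 4, E = 4 N/cm², r = 0.5, A = 0):

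- Var(Y) = 25 + 16 + 32 = 73; c = −66; VA = 260; VC = 160.
- V1 = 73 − 4356/260 = 56.2. V2 = 73 − 4356 × 160/(41600 − 20736) = 39.6. The CI is about 16% narrower.
- Here the planned covariate already removes 16.8/73 = 23% of the variance, so it does more work than for circumference.

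Over F 8-16, S 6-10, r 0.3-0.7, U 4-8 and E = 4, the narrowing is 3-27%. Other plausible inputs for error and asymmetry move the ends to roughly 2% and 34%.

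**Validity of the planned model.** In 4,000 simulated trials at 120 per arm under the central circumference inputs, the planned model gave mean estimates of −0.001 (true 0) and 0.200 (true 0.2), with coverage of 94-95%.

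**The case against.** The strongest reply is that nothing is broken. Under randomization, ANCOVA on an endpoint's own baseline is valid, and the simulation confirms it. A reader might infer that mixing foot size with injury confounds the comparison; it does not, because both are balanced in expectation and the only cost is precision. Study success rests on Day 5 pain on movement alone (Protocol 3), so no stated decision depends on these intervals. All of this stands.

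A reader might also infer that the protocol itself demands the contralateral covariate. It does not. Protocol 9.2.1 and 9.2.3 describe comparing the two sides, and the plan carries that out through the side-difference endpoints. Those endpoints recover part of the information. In the central case, adjusted for their own baseline difference, their residual variance is 0.16 + 0.16 + 0.08 − 0.32²/0.72 = 0.258, so the CI is about 18% narrower than for the planned change endpoint (√(0.258/0.387) = 0.82).

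Two things limit this reply. The change endpoints are still reported with their own intervals, which the companion endpoints do not alter. And neither document names the baseline side difference as the companion covariate: those endpoints are defined only on Days 3, 5 and 8, and the protocol restricts the covariate to outcomes that have a baseline.

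Finally, the size of the gain is assumed. That stands too: the direction is firm, the percentage is not.

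**Conclusion.** This is a worthwhile improvement in precision for two secondary endpoints, not an error or a bias. The planned intervals have correct coverage but are wider than the collected data allow. The narrowing is roughly 2-57% for circumference (central cases about 16-25%) and roughly 2-34% for tenderness. It depends mainly on measurement error and between-subject variation in recovery, for which the documents give no values. The gain was positive in every scenario examined.

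It would be too strong to say that the planned covariate is useless. It usually explains little of the change in circumference, but up to 18% in the grid above, and more for tenderness. For tenderness the point also assumes that the contralateral Visit 1 reading was recorded, which the documents imply rather than state.

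**What to change.** In Protocol 12.2.6 and SAP 4.6.1, before unblinding:

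1. Add the contralateral ankle's Visit 1 value as a second covariate in the ANCOVAs for change in circumference and change in tenderness.
2. For circumference, the baseline side-to-side difference may replace the single covariate with nearly the same result. For tenderness, keep the two baselines as separate covariates, since the injury deficit may scale with a person's usual threshold and the best weights need not be equal and opposite.
3. State that the covariate for the side-difference endpoints is the baseline side-to-side difference.
4. Confirm that contralateral tenderness is recorded at Visit 1.

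The cost is one degree of freedom per change model among about 240 subjects, with no new measurement and no change to any endpoint. The choice should be fixed before unblinding, because a covariate picked afterwards is open to challenge.
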